6.4. Visit Windows

There will be no derivation for visit windows in terms of summary assessments. Nominal visits will be used for by-visit tables.

For data with repeated observations at a given visit, for example, laboratory assessments, the earliest of the available non-missing values at a visit should be used in summary tables. Other observations will be considered as unscheduled visits. For the purpose of tabulations, the unscheduled post-baseline values generally will be excluded from summary tables, but will be included in the listing. Unscheduled visits will be considered for analyses of worst CTCAE laboratory grades.

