9.3. Laboratory Evaluations

Laboratory measurements (hematology, chemistry, urinalysis, and coagulation) obtained at baseline and each study visit will be summarized by dose group in the following ways:

- Descriptive statistics of actual results and changes from baseline (number of subjects, mean, standard deviation, median, minimum, and maximum) for the continuous data and frequencies and percentages for the categorical data, for each assessment visit

This document is confidential.

- Potentially clinically significant lab abnormalities for hematology, chemistry and coagulation will be summarized by study part, dose group and assessment visit.
- By-subject line plots will be presented by lab parameter, study part and dose group, to allow for significant out of range values to be further identified

By-subject safety laboratory listings will be generated incorporating information and assessment results obtained from the designated laboratory which provided normal range and reported out of range results. All laboratory results in SI units will be presented in data listings. Tests will be listed in alphabetical order within their respective panels (hematology, serum chemistry, urinalysis, and coagulation).

Potentially clinically significant hematology and chemistry laboratory results will be summarized using severity grades according to NCI CTCAE (version 5.0 or higher) where applicable. The worst post-baseline severity grade will be summarized and is defined as the most severe toxicity grade of the specific parameter assessed during the study at a scheduled or unscheduled visit. If a severity grade scale is missing for a laboratory parameter, the normal ranges of the clinical laboratory will be used.

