9.5. ECG

A 12-lead ECG will be performed locally at the site, and obtained at Screening, and pre-dose and 1 hour post dose on Day 1 for all subjects.

A shift table of the investigators' assessment of ECG results at each visit compared with baseline values will be presented by treatment group using the following categories: normal; abnormal (not clinically significant); abnormal (clinically significant). The number and percentage of subjects in each cross-classification group of the shift table will be presented by dose group and overall. Subjects with a missing value at baseline or post baseline will not be included in the denominator for percentage calculation.

A by-subject listing will be provided, including each ECG parameter: ventricular heart rate (beats per minute [bpm]), PR interval [msec], RR interval [msec], QRS Duration [msec], QT interval [msec], QTcB interval [msec], QTcF interval [msec] and investigator's interpretation. Potentially clinically significant QTcF values will be flagged in the listing.

The number and percentage of participants with PCS and potentially clinically significant change (PCSC) values will be summarized by visit/timepoint and for any time post-baseline. Potentially clinically significant values will be identified for ECG parameters as outlined below.

Table 10.5.1: Potentially Clinically Significant Values for QT, QTcF, QTcB

This document is confidential.

ECG Parameter	Units	Criteria for PCS Values (Observed values)		Criteria for PCS values (Change from Baseline values)	
		High	Low	Increase	Decrease
QT, QTcF	msec	>450 but <=480 >480 but <=500 >500	NA	>=30 to 60 >60	NA

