9.7. Spirometry

Spirometry assessments FEV₁, FVC, and FEF₂₅₋₇₅ will be collected to evaluate for provoked bronchospasm. Actual liter values will be recorded. Details regarding spirometry procedures and standards will be included in the Study Manual.

Observed values and mean changes from baseline will be presented for each spirometry parameter using descriptive statistics (i.e. n, mean, standard deviation, median, minimum, and maximum) by dose group and visit, using the Safety population. If multiple measurements are to be performed at each time point, the highest value will be used for analysis.

A by-subject listing will be provided, including each spirometry parameter, and will be sorted by subject and visit.

A by-subject line plot will be presented by spirometry parameter, study part and dose group. Each dose group will be on a new plot, with all subjects of the same dose group on the same plot. Any unscheduled results will also be part of this plot.

The number and percentage of participants with PCS values will be summarized by visit/timepoint and for any time post-baseline. Potentially clinically significant values will be identified for FEV₁ (forced expiratory volume) as outlined below.

Table 10.7: Potentially Clinically Significant Values for Forced Expiratory Volume Decrease

Parameter	Units	Criteria for PCS Values (Observed values)	
		High	Low
Forced Expiratory Volume	%	NA	70 – 99 60 – <70 50 – <60 <50

This document is confidential.

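### By default, the any-time-post-baseline ECG and FEV₁ counts in SAP 9.5 and 9.7 leave out unscheduled values, because 6.4 makes an exception only for worst CTCAE laboratory grade

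*SAP*

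**What the plan says.** Section 6.4 sets the general rule. By-visit tables use nominal visits. Where a visit has repeat observations, the earliest non-missing one is used, and "Other observations will be considered as unscheduled visits". For tabulation, "the unscheduled post-baseline values generally will be excluded from summary tables, but will be included in the listing". The next sentence gives the only named exception: "Unscheduled visits will be considered for analyses of worst CTCAE laboratory grades". Section 9.3 repeats it, defining the worst post-baseline laboratory grade as the "most severe toxicity grade of the specific parameter assessed during the study at a scheduled or unscheduled visit".

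Sections 9.5 and 9.7 each promise a count that is not tied to a visit. For ECG, PCS values and PCS changes "will be summarized by visit/timepoint and for any time post-baseline". For spirometry, "The number and percentage of participants with PCS values will be summarized by visit/timepoint and for any time post-baseline". Neither section says whether unscheduled values enter the any-time count.

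Section 9.7 also says that spirometry parameters "will be collected to evaluate for provoked bronchospasm". It takes the highest of multiple measurements at a time point and, for the by-subject line plot, adds: "Any unscheduled results will also be part of this plot".

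**The concern.** An any-time count is meant to catch an abnormal value whenever it occurred. If it is built from scheduled time points only, it misses the measurements taken because something happened between them. Those are also the values most likely to be abnormal. Laboratory data are protected from this by an explicit exception; ECG and FEV₁ are not.

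Two supportive safety tables are at stake. Acute bronchospasm is an AE of interest in 9.2.1, and spirometry is the measurement collected to detect it. A low FEV₁ on an extra test that was not also reported as an adverse event would appear in a listing and on a plot, but in no summary table.

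**Working it through.** The SAP gives no figure to reproduce, so the check is a comparison of sections followed by simple arithmetic.

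**1. Which rule applies.**
- General rule (6.4): unscheduled post-baseline values are generally out of summary tables and in listings.
- Named exception (6.4, repeated in 9.3): worst CTCAE laboratory grade.
- ECG any-time count (9.5): no mention of unscheduled values.
- FEV₁ any-time count (9.7): no mention of unscheduled values, although the line plot in the same section explicitly includes them.

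Where the authors wanted unscheduled values in an output (laboratory grades, spirometry plot), they said so. A programmer who follows 6.4 would leave them out of the two any-time counts.

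**2. What the ECG row then contains.** Section 9.5 schedules ECGs at Screening, Day 1 pre-dose and Day 1 one hour post-dose. Section 6.2.1 defines baseline as the last non-missing value before first dose. Scheduled post-baseline ECGs: 3 − 2 = 1. With scheduled values only, the any-time row equals the Day 1 one-hour row for every subject, although MAD dosing runs 5 days (Cohort 3) or 10 days (Cohort 4).

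**3. Direction of the error.** A subject counts if at least one eligible value meets the criterion. Adding values can turn a no into a yes, never the reverse. Omitting them can therefore only lower the number of subjects with any PCS value, or the number at or beyond a given severity band. A milder band on its own could lose a subject who moves to a worse one. The same direction holds for percentages if the denominator is unchanged.

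**4. Size per affected subject**, at the planned numbers in 3.4.1, 3.4.2 and 3.6:
- Active arm of Cohort 1, 2 or 3: 1/3 = 33.3 percentage points.
- Active arm of Cohort 4: 1/15 = 6.7 points.
- Pooled placebo: 1 + 1 + 1 + 5 = 8 planned, so 1/8 = 12.5 points. It is less once the Amendment 5 placebo subjects are added (6.1); their number is not given.

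These figures are one subject over the group size. They do not predict how many subjects would be affected.

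**5. Interaction with the selection rules.** Section 6.4 keeps the earliest repeat at a visit and labels the others unscheduled. Section 9.7 keeps the highest spirometry value at a time point. If every value labelled unscheduled were simply admitted to the any-time FEV₁ count, lower repeat manoeuvres that 9.7 discards would come back in and inflate it. Any correction has to settle which rule governs.

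**The case against.** The strongest reply is that 6.4 says generally, not always, and that the any-time wording in 9.5 and 9.7 is the more specific text. Set beside a by-visit count, it can naturally be read to include unscheduled values. The ECG schedule supports this, since the any-time row is redundant otherwise. This stands in part: exclusion is the default reading, not an explicit rule for these two tables, and a reader who infers that every table except laboratory grade drops unscheduled values goes beyond the text. It does not remove the problem, because the SAP leaves the choice to the programmer and its only general rule points to exclusion.

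Other stronger readings are also tempting, and the SAP does not support them:

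- **That the primary endpoint is understated.** The primary endpoints are incidence and severity of TEAEs (4.1), which do not depend on visit scheduling. AEs of interest and DLTs are tabulated separately (9.2).
- **That the values are lost.** They remain in the listings, and unscheduled spirometry remains on the line plot.
- **That the ECG count would miss bronchospasm or conflict with the AE-of-interest table.** The ECG criteria in 9.5 are QT and QTcF thresholds, so that count is not expected to track bronchospasm or tachycardia.
- **That a 33-point shift is to be expected.** The SAP gives no frequency for unscheduled measurements. The FEV₁ bands in 9.7 run from 99% down to below 50%, so some subjects may already fall in a band at a scheduled visit. For them an unscheduled value could change the worst band but not the count of subjects with any PCS value.

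**Conclusion.** The point holds as a gap between the general rule and two specific tables. Under the 6.4 default, the any-time PCS counts for QT/QTcF and FEV₁ omit event-triggered measurements, and the omission has one direction. For ECG, the any-time row adds nothing to the Day 1 one-hour row.

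The consequence is limited to supportive safety counts. It is 33.3 points per affected subject in the active arm of Cohorts 1 to 3 and 6.7 points in Cohort 4, assuming the planned enrolment was reached; 6.1 notes that the sponsor decided to close the study early. How many subjects would be affected cannot be derived from the SAP. The conclusion also assumes that the programmer applies 6.4 wherever a later section is silent. The change is worth making because it extends the SAP's own laboratory approach and uses data already collected.

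**What to change.** Add to 6.4, with cross-references in 9.5 and 9.7:

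> Counts of subjects with a PCS or PCSC value at any time after baseline will use values from scheduled and unscheduled post-baseline time points. By-visit rows will use nominal visits only. For spirometry, the highest value within each time point (scheduled or unscheduled) will be selected first, as in 9.7, and the worst of these across time points will then be taken. For spirometry this replaces the earliest-value rule above, and repeat manoeuvres at the same time point are not treated as unscheduled values.

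The last two sentences are needed so that the correction does not admit the repeat manoeuvres that 9.7 sets aside.

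The cost is one short paragraph, two cross-references and a change to two table derivations. No new data are needed. The downside is slightly higher abnormality counts in the any-time rows.

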6.5. Pooling of Centers

Data from all sites will be summarized together for analyses.

6.6. Subgroups

No subgroup analyses are planned for the study.

This document is confidential.

7. Demographic, Other Baseline Characteristics and Medication

7.1. Subject Disposition and Withdrawals

A summary table will be produced detailing the number of subjects screened and screen failed, the number and percentage of all subjects in each analysis population, subjects who completed or discontinued study treatment, subjects who completed or who prematurely discontinued the study. In addition, reasons leading to discontinuation from study and study treatment discontinuation will be summarized for each cohort and overall. A listing of subject disposition will also be provided.

Screened subjects are defined as all subjects with a non-missing informed consent date and screen failures are defined as all subjects who sign the informed consent but are not enrolled into the study.

7.2. Demographic and Other Baseline Characteristics

Descriptive summaries of demographic and baseline characteristics will be presented by each cohort and overall for the Safety Population. The characteristics being summarized include: age at screening (in years), sex, race, ethnicity/geographic origin (north east Asian or south east Asian), height (cm), weight (kg), BMI (kg/m²), and for females, childbearing potential. Baseline disease characteristics include FEV₁ (L), FEV₁ % Predicted, FVC (L), FEF₂₅₋₇₅ (L), sweat chloride (mEq/L), CFRSD-CRISS score, and CFQ-R Respiratory Symptoms Score.

Height (in cm) = height (in inches) * 2.54

Weight (in kg) = weight (in lbs) * 0.4536

BMI (kg/m²) = Weight(kg)/[Height(m)²]

Demographics and Baseline characteristics will be listed by subject for the Safety Population.

7.3. Medical History

Medical History will be summarized for the Safety Population using Medical Dictionary for Regulatory Activities (MedDRA) system organ class (SOC) and preferred term (PT). The reported medical history terms will be coded using MedDRA Version 23.0 or higher. The number of subjects with any medical or surgical history will also be summarized. A subject experiencing a medical history within more than one SOC and PT will be counted only once within that SOC and PT, respectively.

Medical history findings will be listed by subject using the Safety Population.

7.4. Medication

Medications will be classified as prior (started prior and did not continue past the first dose of study treatment) and concomitant (continued past or started on or after the first dose date of study treatment).

All prior and concomitant medications will be classified using the Anatomical Therapeutic Chemical (ATC) classification codes and preferred drug names from the World Health Organization Drug Dictionary (WHO-DD), March 2020.

Summaries of prior and concomitant medications will be presented separately in tabular form using the ATC 4 level term as an upper classification level and the preferred drug name as a lower classification level. All medications will be summarized by descending frequency of ATC level 4 and preferred drug

This document is confidential.

name within a given ATC level 4 term. The summary will consist of the frequency and percent of safety subjects who used the medication at least once.

For each subject, the medication will be counted only once within a level-4 ATC and only once within a given preferred drug name level. A subject may appear more than once if he/she has more than one concomitant medication coded under different ATC categories; however, the subject will be counted only once in the overall category.

A by-subject listing with coded terms will also be provided along with calculated study day.

7.4.1. Prior Medication

Any medication that started prior and did not continue past the first dose of study treatment will be classified as prior.

7.4.2. Concomitant Medication

Concomitant medications are defined as all medications taken during the study treatment period, including those which started before study treatment, but were reported ongoing at the first administration.

This document is confidential.

8. Efficacy

Observed values and changes from baseline for each efficacy endpoint in [Sections 4.2 and 4.3](#) will be summarized with descriptive statistics at each scheduled time point based on the Safety Population for each dose cohort. Subjects will be analyzed as members of the treatment group to which they were randomized to.

8.1. Efficacy Endpoint and Analysis

Analysis of change in *P. aeruginosa* CFU per gram of sputum from Baseline through approximately 14 days after the last study drug dose of the MAD cohorts. Analysis of this exploratory endpoint will not be performed by Syneos Health.

8.2. Exploratory Efficacy Endpoint(s) and Analyses

8.2.1. Change in *P. aeruginosa* CFU per gram of sputum from Baseline through Visit 5 for SAD Cohorts

Analysis of this exploratory endpoint will not be performed by Syneos Health.

8.2.2. Change in *P. aeruginosa* isolates' sensitivity to AP-PA02 and/or its individual components

Analysis of this exploratory endpoint will not be performed by Syneos Health.

8.2.3. Change in *P. aeruginosa* isolates' sensitivity to antipseudomonal antibiotics

Analysis of this exploratory endpoint will not be performed by Syneos Health.

8.2.4. Change in Cystic Fibrosis Questionnaire-Revised (CFQ-R) from Day 1 pre-dose through end of study

Cystic Fibrosis Questionnaire-Revised (CFQ-R) subject health-related quality of life questionnaire assesses 12 domains: physical functioning, role functioning, vitality, emotional functioning, social functioning, body image, eating problems, treatment burden, health perceptions, weight, respiratory symptoms, and digestive symptoms.

Each domain is composed of a variable number of self-report questions with distinct 4-point Likert scales (e.g., always/often/ sometime/never), with a total of 50 questions. CFQ-R general scoring instructions are provided in [Appendix 15.1](#). Each of the CFQ-R domains scores range from 0 to 100, with higher scores indicating a higher patient-reported quality of life with regard to the domain being evaluated. Domain scores are derived only when >50% of domain items are not missing.

The CFQ-R domain scaled score and absolute change from baseline will be summarized by visit using summary statistics for continuous variables by cohort and overall for each study part.

8.2.5. Changes in the Cystic Fibrosis Respiratory Symptom Diary (CFRSD) and Chronic Respiratory Infection Symptom Score (CRISS) from Day 1 pre-dose through the end of the study

The Cystic Fibrosis Respiratory Symptom Diary – Chronic Respiratory Infection Symptom Score (CFRSD-CRISS) is a subject-reported outcome that measures respiratory symptoms in cystic fibrosis using standard qualitative methods, includes 16 questions (8 symptom items, 4 emotional impact items, and 4 activity impact items) and takes less than 5 minutes to complete.

This document is confidential.

The eight respiratory symptom items will be rescored, summed, and converted to a 0 to 100 scale using the scoring guidelines of the Cystic Fibrosis Respiratory Symptom Diary (CFRSD) and Chronic Respiratory Infection Symptom Scale (CFRSD-CRISS), Version 2.0, 8 September 2016. The CFRSD-CRISS will not be calculated if more than one item response is missing. Scoring of the emotional and activity impact items is still under development and will not be summarized. The rescaling schema and conversion table are provided in [Appendix 15.2](#). CFRSD severity score and absolute changes from baseline will be summarized for visits 2 through 6/EOS for SAD cohorts, and visits 2 through 8/EOS for MAD cohorts using summary statistics.

For SAD Visits 3, 4, 5, 6 and MAD Visits 6, 7, 8, 9 for Cohort 3 and MAD visits 11, 12, 13, and 14 for Cohort 4 under Protocol Version 6, there will be multiple days of diary data. The average daily score will be calculated for these multiple days and presented for a single visit corresponding to the Schedule of Assessments in Appendix 1 of the Protocol. Results for Daily Symptom Diary will be grouped to a single study visit if it occurs on the day of the study visit up until the day before the next visit is performed. For example, if a subject's Visit 3 occurs on Study Day 3, and Visit 4 occurs on Study Day 8, then the Daily Symptom Diary results for Study Day 3, 4, 5, 6, and 7 will be averaged and summarized for Visit 3.

This document is confidential.

9. Safety

The population used for safety analyses will be the Safety Population. Safety will be assessed on the basis of treatment emergent adverse event (TEAE), dose-limiting toxicities (DLTs), vital signs, laboratory assessments, immunogenicity, electrocardiogram (ECG) parameters, and physical examinations.

All safety information will be provided in subject listings.

9.1. Extent of Exposure

AP-PA-02 will be administered as a 3 mL loading volume for inhalation via the study nebulizer. Duration of treatment for SAD cohorts 1 and 2 will be one day and for the MAD cohorts 3 and 4 –two fractionated doses administered on five and ten consecutive days respectively (each of the two doses of a dose level is fractionated over two administrations).

Study drug exposure will be summarized using the treatment duration (days), total dose administration time (minutes), and number of doses for the Safety Population. Treatment duration is the number of days between first and last study drug inhalation, defined as last inhalation date – first inhalation date + 1. Total dose administration time for SAD cohorts is the elapsed time between start time and stop time of study drug administration, defined as stop time (HH:MM) – start time (HH:MM), and will include dose interruption or delay, if any occurred. Total dose administration time for MAD cohorts is defined similarly to SAD cohorts, for each dosing day, and for only the first dose of the day. Continuous variables will be summarized with descriptive statistics of mean, SD, median, minimum, and maximum.

9.2. Adverse Events

An overall summary of TEAEs will be provided, including the number and percentage of subjects who experience at least one of the following will be summarized by dose cohort and overall for each study part:

- TEAEs
- Serious TEAEs
- TEAEs related to study drug
- TEAEs related to study device
- TEAEs related to study procedure
- Serious TEAEs related to study drug
- Serious TEAEs related to study device
- Serious TEAEs related to study procedure
- TEAEs leading to permanent withdrawal of study drug
- TEAEs related to study drug leading to permanent withdrawal of study drug
- TEAEs of interest
- DLTs
- TEAEs with Grade 1 (Mild) as Worst Severity
- TEAEs with Grade 2 (Moderate) as Worst Severity

This document is confidential.

- TEAEs with Grade 3 (Severe) as Worst Severity
- TEAEs with Grade 4 (Life-Threatening) as Worst Severity
- TEAEs leading to death

The number and incidence of events will be provided in the overall summary table by dose cohort and overall for each study part.

TEAEs are defined as an adverse event that was not present prior to administration of the first dose of study drug and subsequently presented after the first dose, or any exacerbation occurring after first dose of an event that was present prior to the first dose.

All AEs will be listed by subject and chronologically by date of AE onset, and by study part, dose group, and subject. This listing will include all data collected in the eCRF and the coded variables. AE dates will be listed as recorded in the eCRF. AEs will be classified by System Organ Class (SOC) and Preferred Term (PT) using MedDRA Version 23.0. Subjects are counted only once within each SOC and PT. TEAEs will be presented by descending frequency by SOC and PT.

Further, the following TEAE summaries will be provided and summarized by dose cohort and overall for each study part:

- Any TEAEs overall and by SOC and PT
- Serious TEAEs, overall and by SOC and PT
- Study Drug-related TEAEs overall and by SOC and PT
- Study Device-related TEAEs overall and by SOC and PT
- Study Procedure-related TEAEs overall and by SOC and PT
- Serious TEAEs related to Study Drug, overall and by SOC and PT
- Serious TEAEs related to Study Device, overall and by SOC and PT
- Serious TEAEs related to Study Procedure, overall and by SOC and PT
- TEAEs by worst severity, overall and by SOC and PT
- Study Drug-related TEAEs by maximum severity, overall and by SOC and PT
- TEAEs leading to permanent withdrawal of study drug, overall and by SOC and PT
- Study Drug-related TEAEs leading to permanent withdrawal of study drug, overall and by SOC and PT
- TEAEs of Interest by SOC and PT
- DLTs by SOC and PT
- DLTs by severity, SOC and PT
- TEAEs which resulted in death, overall and by SOC and PT

If a subject has more than one event within a given SOC or PT at different severities, the maximum severity will be tabulated. For example, if a subject experiences two events with the same preferred term,

This document is confidential.

but one was at moderate and the other at severe severity, the severe TEAE will be included in the tabulation. Severity is classified into five categories: mild, moderate, severe, life-threatening and death.

An AE will be considered drug-related if the relationship attribution designation is missing. AEs with a missing onset date, but with stop date either missing or on or after the date of first dose of study drug will be included as treatment emergent. All AEs will be listed in subject listing, and summarized by numbers and percent of subjects by dose for each portion of the study separately. If a subject reports the occurrence of a particular event more than once, the most severe of those events will be included in the summary tables of TEAEs, and the most severe of the treatment-related events will be included in the summary tables of treatment-related events.

If the severity or relationship to study drug, study device or study procedure, is missing for an AE, the event will be assumed to have severity level of 'severe' or the maximum relationship (i.e. definitely), respectively. If the seriousness status is missing for an AE, the event will be assumed to be serious.

